12.2. Appendix 2: Clinical Laboratory Tests

- The tests detailed in Table 6 will be performed by the local laboratory.
- Protocol-specific requirements for inclusion or exclusion of participants are detailed in Section 6 of the protocol.
- Additional tests may be performed at any time during the study as determined necessary by the investigator or required by local regulations.

Table 6	Protocol-Required Safety Laboratory Assessments

elet Count C Count moglobin matocrit od Urea ogen (BUN)	Pota	RBC Indices: MCV MCH %Reticulocytes	Aspartate	Diffe Neut Lymp Mone Eosi	C count with rential: trophils phocytes ocytes nophils ophils Total and
C Count moglobin matocrit od Urea	Pota	MCV MCH %Reticulocytes		Diffe Neut Lymp Mone Eosi	rential: trophils phocytes ocytes nophils ophils
	Pota	assium			Total and
	Pota	assium			Total and
			Aminotransfer (AST)/ Serum Glutamic- Oxaloacetic Transaminase (SGOT)	1	direct bilirubin
atinine	Sod	lium	(ALT)/ Serum Glutamic-Pyru	n uvic	Total Protein
	-		Cholesterol ^{2,3}		Low Density Lipoprotein ^{2,3}
lycerides ^{2,3}	Gan	nma-glutamyl	Creatine kina (CK) ⁴	se	
	cium lycerides ^{2,3}	cium Alka pho lycerides ^{2,3} Gar tran	sium Alkaline phosphatase	Alkaline phosphatase lycerides ^{2,3} Glutamic- Oxaloacetic Transaminase (SGOT) Alanine Aminotransfe (ALT)/ Serun Glutamic-Pyre Transaminase (SGPT) Cholesterol ^{2,3} Creatine kina (CK) ⁴	atinine Sodium Alanine atinine Sodium Alanine Aminotransferase (ALT)/ Serum Glutamic-Oxaloacetic Transaminase (ALT)/ Serum Glutamic-Pyruvic Transaminase (SGPT) cium Alkaline phosphatase Cholesterol ^{2,3} lycerides ^{2,3} Gamma-glutamyl transferase (GGT) ⁴ Creatine kinase

• pH, glucose, protein, blood, ketones, by dipstick

• Microscopic examination (if blood or protein is abnormal)

Laboratory Assessments

Parameters

Other Clinical Laboratory Tests

- alcohol breath test and urine drug screen (to include at minimum: amphetamines, barbiturates, cocaine, opiates, cannabinoids and benzodiazepines)
- Serology (HIV antibody, hepatitis B surface antigen [HBsAg], and hepatitis C virus antibody)
- Urine cotinine

The results of each test will be loaded electronically into the eCRF.

NOTES:

- Details of liver chemistry stopping criteria and required actions and follow-up assessments after liver stopping or monitoring event are given in Section 8.1 and Appendix 7 All events of ALT ≥3 × upper limit of normal (ULN) and bilirubin ≥2 × ULN (>35% direct bilirubin) or ALT ≥3 × ULN and international normalized ratio (INR) >1.5, if INR measured, which may indicate severe liver injury (possible Hy's Law), must be reported as an SAE (excluding studies of hepatic impairment or cirrhosis).
- 2. In Part C at certain time points as per the SoA lipids and glucose samples are required to be taken fasted.
- 3. Screening samples are required to be taken fasted.
- 4. To be analysed at screening, Day-1 and follow up only

Laboratory/analyte results that could unblind the study will not be reported to investigative sites or other blinded personnel until the study has been unblinded.

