Kidney function	 Non-adverse increased urinary glucose concentration was seen in female monkeys and rats given ≥10 mg/kg/day. Other clinical pathology that may be related to perturbations in kidney function were seen in monkeys or rats. Monkeys given ≥3 mg/kg/day for 6 weeks had decreased plasma albumin; rats given ≥10 mg/kg/day for 6 weeks had decreased urinary volume, lower urinary total protein and protein concentrations, variable changes in plasma creatinine concentration and urea, higher glucose and phosphorus concentrations and slightly lower sodium, 	 Participant Selection / Monitoring/ Stopping Criteria: Specific eligibility - criteria (see Section 6.2). The protocol includes laboratory assessments for renal function, electrolytes, fasting glucose, as well as urinary glucose assessment. Relevant renal and glycaemic safety data from the current and any previous cohort will be considered as part of dose escalation decisions.

Potential Risk of Clinical Significance	Summary of Data / Rationale for Risk	Mitigation Strategy
	 potassium and chloride concentrations. No histological changes were seen in the kidneys of monkeys given GSK3358699. Tubular dilatation and higher kidney weight was evident at the non-tolerated 100 mg/kg/day dose in male rats. Some of the urinary effects in rats are evident below the maximum predicted human exposure (AUC) at 45 mg and the NOEL in monkeys at or below parity to the maximum predicted human exposure (AUC) at 45 mg. 	

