Testicular	 No testicular findings were observed in monkeys dosed up to 6 weeks at the maximum tolerated dose of 10 mg/kg/day. In the rat, testicular findings (sperm retention and/or minimal to slight germ cell degeneration, tubular vacuolation and multinucleate germ cells) were evident at non-tolerated doses of ≥100 mg/kg/day with an 8-fold margin from the maximum predicted human exposure (AUC) at 45 mg to the NOAEL for testicular effects. 	 Dose Selection: Doses administered as part of this study will not intentionally exceed the GSK3358699 AUC of 255 ng/ml.h, Cmax 42 ng/ml which are the predicted AUC and Cmax at 45 mg QD. Participant Selection / Monitoring: AE reporting will be used to identify and assess any signs and symptoms related to testicular safety. Appropriate contraceptive measures for participants is included in Section 6.1 and Section 12.5. Relevant safety data from the current and any previous cohort will be considered as part of dose escalation decisions.
Aneugenicity	 GSK3358699 has been determined to be an aneugen with a 7fold margin to the maximum predicted human exposure (C_{max}) at 45 mg to the NOEL for aneugenicity in rats. GSK3359699 is derived from a series of benzimidazoles. Benzimidazoles as a class are known aneugens and the rodent carcinogenicity data and clinical exposure data for benzimidazoles indicates that there is no evidence for translation of the observed aneuploidy in to a carcinogenic risk for humans. 	Dose Selection: • Doses administered as part of this study will not intentionally exceed the GSK3358699 AUC of 255 ng/ml.h, C _{max} 42 ng/ml which are the predicted AUC and C _{max} at 45 mg QD.
Haematologic	 Variable changes in red blood cell parameters were noted at non-tolerated doses in both rats and monkeys. At tolerated doses, no hematological changes were seen in monkey and increased red cell distribution width (RDW), reticulocytes and/or MCV were seen in rats. No microscopic changes were observed in the hematopoietic and lymphoid organs of monkeys and those evident in rats given ≥ 100 mg/kg/day were considered 	 Dose Selection: Doses administered as part of this study will not intentionally exceed the GSK3358699 AUC of 255 ng/ml.h, Cmax 42 ng/ml which are the predicted AUC and Cmax at 45 mg QD. Participant Selection / Monitoring / Stopping Criteria: Specific eligibility and withdrawal criteria (see Section 6.2

Potential Risk of Clinical Significance	Summary of Data / Rationale for Risk	Mitigation Strategy

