	 non-adverse. Further details are in the IB Section 2. Decreases in platelet count were not observed preclinically with GSK3358699 but have been observed with panBET inhibitors in the clinic. 	 and Section 8). The protocol includes laboratory haematological assessments. Relevant haematological safety data from the current and any previous cohort will be considered as part of dose escalation decisions.
Hepatic	 Findings in the liver of monkeys dosed for 6 weeks consisted of non-adverse centrilobular vacuolation in a single animal given 10 mg/kg/day. Cytoplasmic rarefaction, hepatocellular hypertrophy and microvesicular vacuolation were seen in dose ranging monkey study. Non-adverse effects were also seen in rats given 100 mg/kg/day for 6 weeks and included cytoplasmic vacuolation, cytoplasmic basophilia and decreased inflammatory infiltration. Clinical pathology changes potentially related to the liver findings include higher alkaline phosphatase (ALP) and aspartate aminotransferase (AST) activities in rats given 100 mg/kg/day. Increases in total bilirubin was also evident in rats given 100 mg/kg/day. There was no evidence of hepatobiliary damage in any toxicology studies conducted with GSK3358699. There is approximate parity and a 7- fold margin from the maximum predicted human exposure (AUC) at 45 mg to the NOEL for liver effects in monkeys and rats respectively. 	 Dose Selection: Doses administered as part of this study will not intentionally exceed the GSK3358699 AUC of 255 ng/ml.h, Cmax 42 ng/ml which are the predicted AUC and Cmax at 45 mg QD. Participant Selection / Monitoring / Stopping Criteria: Specific eligibility and withdrawal criteria (see Section 6.2 and Section 8). The protocol includes laboratory liver chemistry assessments. Relevant liver safety data from the current and any previous cohort will be considered as part of dose escalation decisions.

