8.2. Clinical Laboratory Analyses

Laboratory evaluations will be based on GSK Core Data Standards and will include:

- Hematology laboratory tests
- Chemistry laboratory tests
- Urinalysis
- Liver function tests
- Other screening tests

Clinical laboratory analyses will include all assessments post-baseline. Unscheduled visits will not be included in summary tables and figures, but will be included in listings – see Section 13.4.2.

Details of the planned displays are presented in Appendix 9: List of Data Displays.

The laboratory assessments for each category are displayed below (Table 6 of the protocol):

Laboratory Assessments		Para	meters			
Haematology						
Clotting parameters: APTT PT times Fibrinogen	Platelet Count RBC Count Haemoglobin Haematocrit	RBC Indices: MCV MCH %Reticulocyte	MCV		WBC count with Differential: Neutrophils Lymphocytes Monocytes Eosinophils Basophils	
Clinical Chemis	strv ¹				1	
CRP	Blood Urea Nitrogen (BUN)	Potassium	Aspartate Aminotransfer (AST)/ Serum Glutamic- Oxaloacetic Transaminase (SGOT)		Total and direct bilirubin	
Albumin	Creatinine	Sodium	Alanine Aminotransfer (ALT)/ Serun Glutamic-Pyru Transaminase (SGPT)	1	Total Protein	
Glucose (fasting during Part C ²)	Calcium	Alkaline phosphatase	Cholesterol ^{2,3}		Low Density Lipoprotein ^{2,3}	
High Density Lipoprotein ^{2,3}	Triglycerides ^{2,3}	Gamma- glutamyl	Creatine kinas (CK) ⁴	e		

207546

Laboratory Assessments	Parameters		
	transferase (GGT) ⁴		
Routine Urinaly	vsis		
• Microscopic e	xamination (if blood or protein is a	bnormal)	

- 1. NOTES:
- Details of liver chemistry stopping criteria and required actions and follow-up assessments after liver stopping or monitoring event are given in Section 8.1 and Appendix 7 of the protocol. All events of ALT ≥3 × upper limit of normal (ULN) and bilirubin ≥2 × ULN (>35% direct bilirubin) or ALT ≥3 × ULN and international normalized ratio (INR) >1.5, if INR measured, which may indicate severe liver injury (possible Hy's Law), must be reported as an SAE (excluding studies of hepatic impairment or cirrhosis).
- 2. In Part C at certain time points as per the SoA lipids and glucose samples are required to be taken fasted.
- 3. Screening samples are required to be taken fasted.
- 4. To be analysed at screening, Day-1 and follow up only 1.

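### The required safety panel (Protocol Table 6) has no chloride, phosphate or RDW, three findings that Section 3.3.1 names for this drug in rats, so they have no scheduled measurement and no planned summary

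*Protocol*

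**What the plan says.** The kidney-function row of Protocol Section 3.3.1 describes rats given at least 10 mg/kg/day for 6 weeks. Among other changes it lists "higher glucose and phosphorus concentrations and slightly lower sodium", continuing with "potassium and chloride concentrations". The mitigation beside it reads: "The protocol includes laboratory assessments for renal function, electrolytes, fasting glucose, as well as urinary glucose assessment". The individual electrolytes are not listed.

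The haematologic row says that at tolerated doses "increased red cell distribution width (RDW), reticulocytes and/or MCV were seen in rats", while monkeys showed no haematological change at tolerated doses. Its mitigation is general: "The protocol includes laboratory haematological assessments".

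Appendix 2 (Section 12.2) turns these commitments into a panel: "The tests detailed in Table 6 will be performed by the local laboratory". Its red-cell entry is "RBC Indices: MCV MCH %Reticulocytes". Section 9.4.7 makes Appendix 2 the definition of the protocol-required laboratory tests. Appendix 2 also lets the investigator order further tests at any time if judged necessary.

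SAP Section 8.2 repeats the panel: "The laboratory assessments for each category are displayed below (Table 6 of the protocol". SAP Section 13.7.2 gives the normal ranges and limits of potential clinical importance that drive the worst-case tables.

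**The concern.** Laboratory safety data are one component of the primary endpoint, and Section 3.3.1 says that relevant renal and haematological data will inform dose escalation. A first-in-human panel would be expected to carry the preclinical signals that its own risk table names, or to say why a named signal is not followed. Other rows do carry across: PT, APTT and fibrinogen (coagulation), triglycerides and cholesterol (lipids), and ALP, AST and total bilirubin (hepatic) are all in Table 6. Chloride, phosphate and RDW are not, and no reason is given.

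What is at stake is the planned comparison of these three measures with baseline and with placebo. Without scheduled values, the study report cannot say systematically whether these rat findings appear in the men dosed.

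**Working it through.** No sample-size, power or error-rate calculation applies, and the plan gives no figure to reproduce. The check sets the analytes named in Section 3.3.1 against the panel. The extracted Protocol Table 6 is broken, so its more legible copy in SAP 8.2 and the limits in SAP 13.7.2 were read as well.

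| Measure named in 3.3.1 | Row | In Table 6 / SAP 8.2 | Limit in SAP 13.7.2 |
|---|---|---|---|
| Sodium | Kidney | Yes | Yes |
| Potassium | Kidney | Yes | Yes |
| Chloride | Kidney | No | No |
| Phosphorus | Kidney | No | No |
| MCV | Haematologic | Yes | Yes |
| Reticulocytes | Haematologic | Yes | Yes |
| RDW | Haematologic | No | No |

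- Electrolytes and minerals in the kidney row: 2 of 4 covered. Glucose, named in the same sentence, is also in the panel, which makes 3 of 5 if it is counted. Calcium is measured but is not named in that row.
- Red-cell measures at tolerated doses: 2 of 3 covered.
- Together, without glucose: 2 + 2 = 4 of 7 covered, and 7 − 4 = 3 missing.

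The protocol table, the SAP copy and the SAP limits all lack the same three, so the broken extraction does not explain the absence.

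Next, what an unscheduled result would contribute. Under SAP Section 5.3 a missing baseline stays missing and no derivation is made. Under SAP Sections 8.2 and 13.4.2 unscheduled visits are listed but left out of summary tables and figures. An extra test ordered after dosing would therefore help in following one participant, but would normally have no pre-dose value and would not enter any planned summary.

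**The case against.** Several points on the other side are sound and set the limits of this one.

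- **Detection is not ruled out.** A reader might infer that the primary endpoint cannot detect these effects, or that no participant will have any data on them. The documents do not support that. Extra tests are allowed at any time, a clinically significant abnormal result is an adverse event, and adverse events are part of the primary endpoint. What is absent is scheduled measurement and planned summary.
- **The matrix is not stated.** The rat sentence moves from urinary measures to plasma creatinine and urea, then lists phosphorus and chloride without saying where they were measured. Plasma is the natural reading, but it is an inference. If they were urinary, serum tests would not track the finding directly; the dipstick would not either, since it covers pH, glucose, protein, blood and ketones.
- **Exposure margins do not transfer.** It is tempting to cite the kidney row's statement about effects below the maximum predicted human AUC at 45 mg. That statement covers only some urinary effects in rats. The monkey no-effect level belongs to monkey findings; those named in the row are urinary glucose and plasma albumin, both of which are measured. Chloride and phosphorus are reported only in rats.
- **RDW contradicts nothing.** The haematologic mitigation promises haematology testing in general, and Table 6 provides it.
- **The signals are modest.** They come from rats, the chloride change is called slight, dosing lasted 6 weeks against at most 14 days in Part C, and related markers (sodium, potassium, BUN, creatinine, MCV, reticulocytes) are measured.

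It can also be said that electrolyte testing without a list promises neither chloride nor phosphate. That is fair as a reading of the wording. Even so, the promise sits beside a row naming four electrolytes or minerals, the panel takes two, and nothing explains the choice.

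**Conclusion.** The point holds as a gap in coverage. Three laboratory findings that the protocol names for this drug in rats are missing from the required panel, so they have no scheduled baseline or post-dose value and no planned summary. The size is 3 of 7 named measures: chloride and phosphate from the kidney row, and RDW from the haematologic row. For the kidney row, the electrolyte mitigation is only partly carried into Table 6. For RDW there is a gap but no inconsistency.

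The conclusion rests on the panel as printed in both documents. The recommendation to add serum chloride and phosphate also assumes that the rat values were plasma values. Closing the gap is a cheap improvement to the primary safety data; leaving it open does not invalidate the plan.

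**What to change.** At the protocol stage, which here means Amendment 4 with Cohorts 5-8 still ahead:

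- Confirm from the Investigator's Brochure whether the rat phosphorus and chloride values were plasma or urinary.
- Add chloride and inorganic phosphate to clinical chemistry, and RDW to the red-cell indices, in Table 6 at the existing time points.
- Carry the three into SAP 8.2 and give them ranges in SAP 13.7.2, so that data so collected enter the change-from-baseline and worst-case tables.
- If the sponsor prefers not to add them, state in Section 3.3.1 why the measured analytes are enough.

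Amendment 4 added GGT and creatine kinase to the same table as extra monitoring, so there is a precedent. The cost is three more results per sample to review and a laboratory charge, assumed small. That the tubes already drawn suffice is also an assumption; the documents do not say.

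A change to the SAP alone cannot recover values that were never scheduled. The SAP was signed on 22 June 2020, after Cohort 5 was terminated on 18 March 2019. For data collected without these analytes, the study report should state the gap as a limitation.

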12.3. Appendix 3: Study Governance Considerations

Regulatory and Ethical Considerations

- This study will be conducted in accordance with the protocol and with:
 - Consensus ethical principles derived from international guidelines including the Declaration of Helsinki and Council for International Organizations of Medical Sciences (CIOMS) International Ethical Guidelines.
 - Applicable ICH Good Clinical Practice (GCP) Guidelines.
 - Applicable laws and regulations.
- The protocol, protocol amendments, ICF, Investigator Brochure, and other relevant documents (eg, advertisements) must be submitted to an IRB/IEC by the investigator and reviewed and approved by the IRB/IEC before the study is initiated.
- Any amendments to the protocol will require IEC/IRB approval before implementation of changes made to the study design, except for changes necessary to eliminate an immediate hazard to study participants.
- The investigator will be responsible for the following:
 - Providing written summaries of the status of the study to the IRB/IEC annually or more frequently in accordance with the requirements, policies, and procedures established by the IRB/EC.
 - Notifying the IRB/IEC of SAE or other significant safety findings as required by IRB/IEC procedures.
 - Providing oversight of the conduct of the study at the site and adherence to requirements of 21 Code of Federal Regulations (CFR), ICH guidelines, the IRB/IEC, European regulation 536/2014 for clinical studies (if applicable), and all other applicable local regulations.

Financial Disclosure

Investigators and sub-investigators will provide the sponsor with sufficient, accurate financial information as requested to allow the sponsor to submit complete and accurate financial certification or disclosure statements to the appropriate regulatory authorities. Investigators are responsible for providing information on financial interests during the course of the study and for 1 year after completion of the study.

Informed Consent Process

• The investigator or his/her representative will explain the nature of the study to the participant or his/her legally authorized representative and answer all questions regarding the study.

- Participants must be informed that their participation is voluntary. Participants or their legally authorized representative will be required to sign a statement of informed consent that meets the requirements of 21 CFR 50, local regulations, ICH guidelines, Health Insurance Portability and Accountability Act (HIPAA) requirements, where applicable, and the IRB/IEC or study centre.
- The medical record must include a statement that written informed consent was obtained before the participant was enrolled in the study and the date the written consent was obtained. The authorized person obtaining the informed consent must also sign the ICF.
- Participants must be re-consented to the most current version of the ICF(s) during their participation in the study.
- A copy of the ICF(s) must be provided to the participant or the participant's legally authorized representative.
- Participants who are rescreened are required to sign a new ICF.

Data Protection

- Participants will be assigned a unique identifier by the sponsor. Any participant records or datasets that are transferred to the sponsor will contain the identifier only; participant names or any information which would make the participant identifiable will not be transferred.
- The participant must be informed that his/her personal study-related data will be used by the sponsor in accordance with local data protection law. The level of disclosure must also be explained to the participant.
- The participant must be informed that his/her medical records may be examined by Clinical Quality Assurance auditors or other authorized personnel appointed by the sponsor, by appropriate IRB/IEC members, and by inspectors from regulatory authorities.

Committees Structure

Dose Escalation Committee

The DEC will make the decision to proceed to the next dose level of GSK3358699 at the end of each single dose (Cohorts 1-2) and repeat dose cohort (Cohorts 4-8); along with making the decision on the dose for Part B of the study and the decision to move into Part C of the study. For details of the information to be considered as part of this decision making process see Section 5.1.

Safety, PK and PD stopping criteria will be strictly applied. Details of these criteria can be found in Section 8. There will be an open and closed part to the dose escalation meeting as required. At the beginning of the meeting blinded data will be discussed in an open forum with the investigator in attendance. If required, the data will then be reviewed in an unblinded fashion by the unblinded members of the DEC. These unblinded members include the Medical Monitor, GSK GCSP representative, GSK

statistician and GSK pharmacokineticist. In instances where the TE data is reviewed the GSK biology representative will also be present at the dose escalation meeting. A DEP will be written outlining in detail how the study team will ensure data integrity used in dose selection decisions by performing clinical data review and appropriate quality control of data prior to making dose selection decisions, as well as outlining the responsibilities of the investigators and site staff for reporting safety data, participation during dose escalation meetings, and confirmation that the data used for dose escalation are accurate and complete.

Publication Policy

- The results of this study may be published or presented at scientific meetings. If this is foreseen, the investigator agrees to submit all manuscripts or abstracts to the sponsor before submission. This allows the sponsor to protect proprietary information and to provide comments.
- The sponsor will comply with the requirements for publication of study results.
- Authorship will be determined by mutual agreement and in line with International Committee of Medical Journal Editors authorship requirements.

Dissemination of Clinical Study Data

- Where required by applicable regulatory requirements, an investigator signatory will be identified for the approval of the clinical study report. The investigator will be provided reasonable access to statistical tables, figures, and relevant reports and will have the opportunity to review the complete study results at a GSK site or other mutually-agreeable location.
- GSK will also provide the investigator with the full summary of the study results. The investigator is encouraged to share the summary results with the study participants, as appropriate.
- GSK will provide the investigator with the randomization codes for their site only after completion of the full statistical analysis.
- The procedures and timing for public disclosure of the results summary and for development of a manuscript for publication will be in accordance with GSK Policy.

Data Quality Assurance

- All participant data relating to the study will be recorded on printed or electronic CRF unless transmitted to the sponsor or designee electronically (eg, laboratory data). The investigator is responsible for verifying that data entries are accurate and correct by physically or electronically signing the CRF.
- The investigator must maintain accurate documentation (source data) that supports the information entered in the CRF.

- The investigator must permit study-related monitoring, audits, IRB/IEC review, and regulatory agency inspections and provide direct access to source data documents.
- The sponsor or designee is responsible for the data management of this study including quality checking of the data.
- Study monitors will perform ongoing source data verification to confirm that data entered into the CRF by authorized site personnel are accurate, complete, and verifiable from source documents; that the safety and rights of participants are being protected; and that the study is being conducted in accordance with the currently approved protocol and any other study agreements, ICH GCP, and all applicable regulatory requirements.
- Records and documents, including signed ICF, pertaining to the conduct of this study must be retained by the investigator for 25 years from the issue of the final CSR/ equivalent summary unless local regulations or institutional policies require a longer retention period. No records may be destroyed during the retention period without the written approval of the sponsor. No records may be transferred to another location or party without written notification to the sponsor.

Source Documents

- Source documents provide evidence for the existence of the participant and substantiate the integrity of the data collected. Source documents are filed at the investigator's site.
- Data reported on the CRF or entered in the eCRF that are transcribed from source documents must be consistent with the source documents or the discrepancies must be explained. The investigator may need to request previous medical records or transfer records, depending on the study. Also, current medical records must be available.
- Definition of what constitutes source data can be found in the Source Document Agreement.

Study and Site Closure

GSK or its designee reserves the right to close the study site or terminate the study at any time for any reason at the sole discretion of GSK. Study sites will be closed upon study completion. A study site is considered closed when all required documents and study supplies have been collected and a study-site closure visit has been performed.

The investigator may initiate study-site closure at any time, provided there is reasonable cause and sufficient notice is given in advance of the intended termination.

Reasons for the early closure of a study site by the sponsor or investigator may include but are not limited to:

2017N332348_05

CONFIDENTIAL

- Failure of the investigator to comply with the protocol, the requirements of the IRB/IEC or local health authorities, the sponsor's procedures, or GCP guidelines.
- Inadequate recruitment of participants by the investigator.
- Discontinuation of further study treatment development.

12.4. Appendix 4: Adverse Events: Definitions and Procedures for Recording, Evaluating, Follow-up, and Reporting

Definition of AE

AE Definition

- An AE is any untoward medical occurrence in a clinical study participant, temporally associated with the use of a study treatment, whether or not considered related to the study treatment.
- NOTE: An AE can therefore be any unfavorable and unintended sign (including an abnormal laboratory finding), symptom, or disease (new or exacerbated) temporally associated with the use of a study treatment.

Events Meeting the AE Definition

- Any abnormal laboratory test results (hematology, clinical chemistry, or urinalysis) or other safety assessments (eg, ECG, radiological scans, vital signs measurements), including those that worsen from baseline, considered clinically significant in the medical and scientific judgment of the investigator (ie, not related to progression of underlying disease).
- Exacerbation of a chronic or intermittent pre-existing condition including either an increase in frequency and/or intensity of the condition.
- New conditions detected or diagnosed after study treatment administration even though it may have been present before the start of the study.
- Signs, symptoms, or the clinical sequelae of a suspected drug-drug interaction.
- Signs, symptoms, or the clinical sequelae of a suspected overdose of either study treatment or a concomitant medication. Overdose per se will not be reported as an AE/SAE unless it is an intentional overdose taken with possible suicidal/self-harming intent. Such overdoses should be reported regardless of sequelae.

Events NOT Meeting the AE Definition

- Any clinically significant abnormal laboratory findings or other abnormal safety assessments which are associated with the underlying disease, unless judged by the investigator to be more severe than expected for the participant's condition.
- The disease/disorder being studied or expected progression, signs, or symptoms of the disease/disorder being studied, unless more severe than expected for the participant's condition.
- Medical or surgical procedure (eg, endoscopy, appendectomy): the condition that leads to the procedure is the AE.
- Situations in which an untoward medical occurrence did not occur (social and/or convenience admission to a hospital).

• Anticipated day-to-day fluctuations of pre-existing disease(s) or condition(s) present or detected at the start of the study that do not worsen.

Definition of SAE

If an event is not an AE per definition above, then it cannot be an SAE even if serious conditions are met (eg, hospitalization for signs/symptoms of the disease under study, death due to progression of disease).

A SAE is defined as any untoward medical occurrence that, at any dose:

a. Results in death

b. Is life-threatening

The term 'life-threatening' in the definition of 'serious' refers to an event in which the participant was at risk of death at the time of the event. It does not refer to an event, which hypothetically might have caused death, if it were more severe.

c. Requires inpatient hospitalization or prolongation of existing hospitalization

In general, hospitalization signifies that the participant has been detained (usually involving at least an overnight stay) at the hospital or emergency ward for observation and/or treatment that would not have been appropriate in the physician's office or outpatient setting. Complications that occur during hospitalization are AE. If a complication prolongs hospitalization or fulfils any other serious criteria, the event is serious. When in doubt as to whether "hospitalization" occurred or was necessary, the AE should be considered serious.

Hospitalization for elective treatment of a pre-existing condition that did not worsen from baseline is not considered an AE.

d. Results in persistent disability/incapacity

- The term disability means a substantial disruption of a person's ability to conduct normal life functions.
- This definition is not intended to include experiences of relatively minor medical significance such as uncomplicated headache, nausea, vomiting, diarrhoea, influenza, and accidental trauma (eg, sprained ankle) which may interfere with or prevent everyday life functions but do not constitute a substantial disruption.

e. Is a congenital anomaly/birth defect

f. Other situations:

• Medical or scientific judgment should be exercised in deciding whether SAE reporting is appropriate in other situations such as important medical events that may not be immediately life-threatening or result in death or hospitalization but may jeopardize the participant or may require medical or surgical intervention to prevent one of the other outcomes listed in the above definition. These events should usually be considered serious.

Examples of such events include invasive or malignant cancers, intensive treatment in an emergency room or at home for allergic bronchospasm, blood dyscrasias or

convulsions that do not result in hospitalization, or development of drug dependency or drug abuse.

Recording AE and SAE

AE and SAE Recording

- When an AE/SAE occurs, it is the responsibility of the investigator to review all documentation (eg, hospital progress notes, laboratory, and diagnostics reports) related to the event.
- The investigator will then record all relevant AE/SAE information in the CRF.
- It is **not** acceptable for the investigator to send photocopies of the participant's medical records to GSK in lieu of completion of the GSK /AE/SAE CRF page.
- There may be instances when copies of medical records for certain cases are requested by GSK. In this case, all participant identifiers, with the exception of the participant number, will be redacted on the copies of the medical records before submission to GSK.
- The investigator will attempt to establish a diagnosis of the event based on signs, symptoms, and/or other clinical information. Whenever possible, the diagnosis (not the individual signs/symptoms) will be documented as the AE/SAE.

Assessment of Intensity

The investigator will make an assessment of intensity for each AE and SAE reported during the study and assign it to 1 of the following categories:

- Mild: An event that is easily tolerated by the participant, causing minimal discomfort and not interfering with everyday activities.
- Moderate: An event that causes sufficiently discomfort and interferes with normal everyday activities.
- Severe: An event that prevents normal everyday activities. An AE that is assessed as severe should not be confused with an SAE. Severe is a category utilized for rating the intensity of an event; and both AE and SAE can be assessed as severe.

An event is defined as 'serious' when it meets at least 1 of the predefined outcomes as described in the definition of an SAE, NOT when it is rated as severe.

Assessment of Causality

- The investigator is obligated to assess the relationship between study treatment and each occurrence of each AE/SAE.
- A "reasonable possibility" of a relationship conveys that there are facts, evidence, and/or arguments to suggest a causal relationship, rather than a relationship cannot be ruled out.
- The investigator will use clinical judgment to determine the relationship.
- Alternative causes, such as underlying disease(s), concomitant therapy, and other risk factors, as well as the temporal relationship of the event to study treatment administration will be considered and investigated.
- The investigator will also consult the IB and/or Product Information, for marketed products, in his/her assessment.
- For each AE/SAE, the investigator must document in the medical notes that he/she has reviewed the AE/SAE and has provided an assessment of causality.
- There may be situations in which an SAE has occurred and the investigator has minimal information to include in the initial report to GSK. However, it is very important that the investigator always make an assessment of causality for every event before the initial transmission of the SAE data to GSK.
- The investigator may change his/her opinion of causality in light of follow-up information and send an SAE follow-up report with the updated causality assessment.
- The causality assessment is one of the criteria used when determining regulatory reporting requirements.

Follow-up of AE and SAE

- The investigator is obligated to perform or arrange for the conduct of supplemental measurements and/or evaluations as medically indicated or as requested by GSK to elucidate the nature and/or causality of the AE or SAE as fully as possible. This may include additional laboratory tests or investigations, histopathological examinations, or consultation with other health care professionals.
- If a participant dies during participation in the study or during a recognized follow-up period, the investigator will provide GSK with a copy of any post-mortem findings including histopathology.
- New or updated information will be recorded in the originally completed CRF.
- The investigator will submit any updated SAE data to GSK within 24 hours of receipt of the information.

Reporting of SAE to GSK

SAE Reporting to GSK via Paper CRF

- Facsimile transmission of the SAE paper CRF is the preferred method to transmit this information to the SAE coordinator.
- In rare circumstances and in the absence of facsimile equipment, notification by telephone is acceptable with a copy of the SAE data collection tool sent by overnight mail or courier service.
- Initial notification via telephone does not replace the need for the investigator to complete and sign the SAE CRF pages within the designated reporting time frames.
- Contacts for SAE reporting can be found in the SRM.

